## 7.0 Recruitment Methods

### **Subject recruitment:**

Since the proposed research investigates stroke recovery it will be supported by the Clinical and Translation Tools and Resources (CTTR) Core of the NIH-funded Center of Biomedical Research Excellence (COBRE) in Stroke Recovery at MUSC. The CTTR Core provides subject recruitment resources through a bioinformatics-enabled database registry. Currently there are more than 900 post-stroke subjects in our database registry and ongoing recruitment is expected to add 1-3 more subjects each week. Additionally, Co-I's on this project have successfully recruited subjects for trials as part of the South Carolina Center for Stroke Recovery Research. Thus, we are confident that recruitment goals will be met without difficulty.

## 8.0 Consent Process

Informed consent will be obtained from participants prior to participation. Participants will first be informed of the purpose of the experiments and possible risks. The PI or an authorized study team member will then review the Informed Consent form with the potential participant, ensuring they are given adequate time to review the document. The potential participant will be asked if they have any questions about the study, and asked if they agree to participate. The Informed Consent and HIPAA forms will be signed by the participant. Copies of the signed forms will be given to the participant. The consent process will take place in a private room in the MUSC College

of Health Professions Research Building. There will be no set period between informing the prospective participant and obtaining the consent. In every session, participants will be reminded that they may end their participation in the study at any point.

## 9.0 Study Design / Methods

**Project Overview.** Subjects will attend 3 initial visits consisting of informed consent, screening, and assessments. All assessments and AEx + DDP sessions will take place in the College of Health Professions Research Building. The AEx + DDP intervention will consist of 18 sessions to be completed within 7 weeks. Subjects will complete 15 minutes of AEx prior to DDP. Sessions will be scheduled up to three times weekly separated by at least 24 hours to allow for adequate rest. After 18 sessions have been completed, post-testing will be scheduled. Any sessions that are not completed within 7 weeks of the first session will be considered missed visits. After completion of the intervention subjects will complete 2 assessment visits. It is expected that the entirety of the study will take approximately 8 weeks to complete (See Figure 3 for study timeline).

[figure not shown]

Figure 3. Study timeline

approximately 8 weeks to complete (See Figure 3 for study timeline).

### Screening and assessment visits

**Screening Assessments:** Following informed consent procedures we will perform screening assessments. Participants will be screened for cognitive function and depression with the Montreal Cognitive Assessment and Patient Health Questionnaire.

- **Montreal Cognitive Assessment (MoCA):** The MoCA is 30-point test used for assessing cognitive impairment. It assesses short-term memory recall, attention and concentration, executive function, language, visuoconstructional skills, orientation, and calculations. Subjects demonstrating cognitive impairment, indicated by a MoCA score < 22 will be excluded.
- **Patient Health Questionnaire (PHQ-9):** The PHQ-9 is a 9-item instrument used for screening and monitoring depression. Since depression has been shown to impact neuroplastic potential, subjects with depression (PHQ-9 > 4) will be excluded.
- **Transcranial Magentic Stimulation (TMS) Screen:** The TMS Screen has been developed from safety guidelines to ensure patients and study participants are safe to receive TMS. If the TMS screen identifies one or more contraindications to TMS subjects will be excluded from receiving TMS assessments.

**Clinical Assessments:** We will perform clinical assessments of UE impairment (FMA-UE), UE function (WMFT), and 'real world' arm use (SIS). This assessment battery is standard to most post-stroke rehabilitation trials. These data will help describe the functional status of participants. A licensed physical therapist, exercise physiologist, or trained study personnel through the South

Carolina Center for Stroke Recovery Research will perform all assessments. These assessments will be performed pre- and post-intervention (Pre Visit 1 and Post Visit 1).

- **Fugl Meyer Upper Extremity Assessment (FMA-UE):** The FMA-UE is a 33-item measure of UE impairment; however, the 3 items testing reflex response will not be administered because they do not measure a voluntary movement construct. Assessments will be video recorded and scored from the videos by trained, blinded raters. Each item will be scored on a 3-point rating scale (0=unable, 1=partial 2=near normal performance), item ratings will be summed and reported out of 60 points so that larger numbers indicate greater UE motor ability. The FMA-UE will be video recorded to allow for scoring by a blinded reviewer.
- **Wolf Motor Function Test (WMFT):** The WMFT is a 15-item measure of UE functional ability. The WMFT will be administered in a standardized manner according to lab specific procedures. Assessments will be video recorded and scored from the videos by trained, blinded raters. Performance of each item will be timed (seconds) and the average time to perform items will be reported so that lower values indicate greater UE function.
- **Stroke Impact Scale (SIS):** The SIS assesses physical function as well as other dimension of health-related quality of life: emotion, communication, memory & thinking, and social role function. Specifically, the Hand and Perceived Recovery subsets of the SIS will be used to assess the effect of the intervention on 'real world' arm use. The SIS-hand consists of 5-items regarding difficulty of paretic hand use during everyday tasks during the previous two weeks. Items will be rated on a 5-point scale (5=not difficult, 1=cannot do) and reported as an average item rating. The SIS-recovery subtest is a single-item in which the participant rates his/her perceived post-stroke recovery from 0%-100% recovered.
- **International Physical Activity Questionnaire (IPAQ):** The IPAQ is a 5-part self-administered physical activity seven-day recall. The IPAQ assesses physical activity frequency, duration, and intensity over the previous seven days in four domains: (1) job-related, (2) transportation, (3) housework and family caring, recreation, (4) sport and leisure. In addition, the fifth domain assesses time spent sitting at work, at home, and during leisure time. The IPAQ has been shown to produce reliable results and validity has been established against accelerometer measurement of physical activity. It is also easily implemented and appropriate for broadly defining physical activity habits.
- **NeuroCom Balance Master™ Test:** Participants will take part in a balance assessment using the NeuroCom Balance Master Sensory Organization Test. This test is able to identify whether balance deficits are due to vestibular, visual, or somatosensory dysfunction. Participants will stand on a force plate, connected to a harness to prevent falls, and participate in several conditions. Participants will be asked to keep their eyes open or closed, depending on the condition, while the force plate they are standing on and/or the walls surrounding them move according to their movements. If participants stay standing still, nothing will move. However, if participants sway, the force plate and/or walls, depending on the condition, will move accordingly. There are 6 conditions: 1) eyes open, everything stable. 2) eyes closed, everything stable. 3) eyes open, force plate moving. 4) eyes closed, force plate moving. 5) eyes open, walls moving. 6) eyes open, force plate and walls moving. All 6 conditions are completed 3 times. In total, the 6 conditions completed 3 times each will take approximately 15-20 minutes.

**Exercise Tolerance Testing:** Prior to experimental visits, a bicycle ergometry protocol modified from the LEAPS trial will be used to assess exercise tolerance prior to study inclusion. The protocol will be overseen by a physician and will commence with the subject seated quietly for two minutes. Exercise will begin with the subject pedaling at ~60 revolutions per minute (RPM) and 0 Watts (W) of workload, with workload will be increased by ~15 W every 3 minutes. If the pedal cadence drops below 50 RPM, additional reminders will be given. Testing continues until maximal effort is achieved. The test will be terminated prior to achieving maximum effort for predefined symptomatic, clinical, and electrocardiographic criteria. Symptom-related reasons for termination include angina, dyspnea, and fatigue. Fatigue is defined as either voluntary exhaustion or inability to maintain a minimum cycling cadence of 40 RPM. Clinical criteria for termination include: 1) Hypertension:  $\geq 220/120$  mmHg, or 2) Hypotension: a drop in diastolic blood pressure  $>20$  mmHg, and O2 saturation  $<85\%$ . Electrocardiogram criteria include: 1)  $\geq 1$  mm horizontal or down sloping ST segment depression, 2) sustained paroxysmal ventricular tachycardia ( $>30$  beats), and 3) sustained paroxysmal supraventricular tachycardia ( $>30$  beats). If the test is terminated because of electrocardiographic findings, the subject will be managed medically as needed, referred for care, and disapproved for participation. Resting blood pressure and heart rate will be obtained prior to initiation of exercise as well as after the subject has been sitting on the stationary bicycle for 1 minute. During the exercise test, blood pressure readings will be obtained every 3 minutes. Heart rate will be obtained from the 12-lead EKG. Maximal heart rate will be recorded as the highest heart rate achieved during the exercise tolerance test.

## Neurophysiological Assessments

- **Assessment of neuroplastic potential:** Participants' neuroplastic potential will be assessed with a plasticity-inducing paradigm called Paired Associative Stimulation (PAS). Briefly, PAS utilizes a repeated and timed peripheral nerve stimulation combined with transcranial magnetic stimulation (TMS) of the contralateral motor cortex to induce motor cortex plasticity. Prior to- and after PAS, corticomotor excitability (CME) is assessed via motor evoked potentials (MEP) which are obtained by single pulse TMS and electromyography (EMG) of a contralateral peripheral muscle. PAS will be assessed pre- and post-intervention (Pre Visit 3, Post Visit 2). PAS will be assessed in the ipsilesional motor cortex and paretic UE.
- **Paired Associative Stimulation:** Prior to PAS, all participants will be assessed for potential contraindications to TMS using a safety-screening questionnaire. First, we will use a combination of on-line surface electromyography (sEMG) recordings to view peak-to-peak motor evoked potential (MEP) amplitude and a neuro-navigation system to identify the optimal coil position for stimulation of the abductor pollicis brevis (APB) muscle (APB 'hotspot'). The area on the hand knob of the motor cortex that produces the largest and most consistent MEP's of the APB muscle will be marked as the 'hotspot' using the neuro- navigation system. We will then assess baseline cortical excitability by collecting a 'bin' of twenty test MEP's and a standardized stimulation intensity. This stimulation intensity will remain the same throughout the experimental session in order to allow for comparisons of MEP amplitude before and after PAS. After assessment of cortical excitability participants will receive PAS. For PAS, participants will receive a combination of simultaneous peripheral nerve stimulation and brain stimulation. Stimulation of the median nerve will be delivered via constant current stimulator (DS7A; Digitimer, Hertfordshire, UK) just proximal to the wrist. Bipolar electrodes will deliver a 200 $\mu$ s square wave pulse at an intensity equal to 300%

sensory threshold. Single pulse TMS will be applied to the APB muscle representation on the contralateral motor cortex 25ms (ISI25) after the delivery of median nerve stimulation. A train/delay generator (DG2A; Digitimer, Hertfordshire, UK) will trigger paired peripheral nerve stimulation and brain stimulation. A total of 200 paired stimuli will be delivered at rate of .25 Hz, resulting in a total stimulation time of approximately 14 minutes. Bins of twenty test MEP's will then be collected immediately, fifteen, and thirty minutes post-PAS.

- **Electromyographic assessment:** Surface electromyography (sEMG) will be collected using 2cm by 2cm surface recording electrodes (Natus, Pleasanton, CA, USA) and will be placed perpendicular to the orientation of the fibers of the APB muscle belly. Prior to sEMG placement the site of the APB muscle will be lightly abraded and cleaned with pre-packaged alcohol swabs. All EMG signals will be collected using Spike2 v7.12 software (Cambridge Electronic Design; Cambridge, UK), amplified (x1000), bandpass-filtered (100-2000 Hz) using a CED 1902 amplifier (Cambridge Electronic Design; Cambridge, UK), and sampled at 5000 Hz using CED Micro 1401-3 data acquisition unit (Cambridge Electronic Design; Cambridge, UK). Data will be saved directly to a network drive for offline analysis. During all stimulation protocols sEMG activity will be continuously monitored in order to ensure that the APB muscle is not voluntarily active.
- **Assessment of DDP-induced CME:** The effect of DDP on CME will be assessed in the paretic UE. Before and after DDP on 3 occasions (DDP sessions 2, 10, and 17) a bin of twenty test MEP's will be collected. If reductions in impairments and improvements in function are mediated by a strengthening of the corticomotor pathway (eg. long-term potential-like response) we would expect DDP to increase CME. While PAS testing will provide information regarding the neuroplastic potential of each subject, this assessment will provide data describing the direct effect of a single and multiple sessions of DDP on the corticomotor pathway of the paretic UE.

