### **Intervention visits**

The AEx + DDP intervention will be a total of 18 sessions to be completed within 7 weeks. Each week, subjects will attend up to 3 sessions of AEx + DDP on non-consecutive days (M, W, F). It is expected that AEx + DDP sessions will last approximately 90 minutes. Post assessment visits will occur after the completion of 18 AEx + DDP session or 7 weeks, whichever occurs first.

**AEx:** Aerobic exercise will be performed on a recumbent stationary cycle (Monark 837e). During AEx, heart rate, blood pressure, and rate of perceived exertion (RPE) will be assessed at baseline, every 5 minutes during exercise (or sitting), immediately post-exercise, and then 5 minutes post-exercise. Exercise intensity will be determined using the Karvonen equation. The Karvonen equation uses an individual's maximum heart rate (MHR) and resting heart rate (RHR) to calculate heart rate reserve (HRR) using the equation:  $HRR = (MHR) - RHR$ . The MHR for each subject will be determined during his/her exercise tolerance test. An exercise physiologist will oversee each AEx session. The target intensity of each AEx session will be 70% HRR and will remain constant throughout the intervention. This intensity was selected for the 'priming' bout of AEx as preliminary results from our lab have shown it has a substantial impact on neuroplastic potential (See Figure 1.a) and serum BDNF in control subjects.

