**DDP:** A therapist will oversee the patient's safety and progress during DDP by: (1) monitoring patient compliance and performance via metrics provided by the Microsoft Kinect system, (2) determining session parameters for all DDP sessions, and (3) continuously monitoring the patient to assess fatigue/pain, answer questions, and problem solve any issues. DDP will be dosed based on the number of repetitions performed. A repetition is recorded when the player moves his/her arm so that the avatar leaves a start position. The goal dose for subjects will be 200 repetitions per DDP session. The number of repetitions was selected because subjects enrolled in our previous studies have averaged 200 self-selected repetitions per day, achieved in ~1 hours without adverse event. Birkenmeir et al (2010) demonstrated that subjects with chronic stroke could safely obtain 200-300 arm movement repetitions in a 1-2 hour therapy session. The therapist overseeing DDP will be permitted to reduce the dose if a subject reports substantial fatigue or pain.

**Participant remuneration:** Study subjects will be paid \$25 per study visit. Subjects may attend up to a total of 23 study visits thus may receive up to \$575 of total compensation for participating in the study. Payments to subjects will be made via ClinCard. Subject will have \$25 added to their ClinCard for each study visit attended.

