**Statistical Analysis Plan:** Feasibility and tolerability metrics of adherence, retention, and acceptability will be assessed (Aim 1). FMA-UE, WMFT, and SIS data will be compared to historical control data from previous DDP trials from [name] lab (Aim 2). We will utilize ANOVAs to test the effect of adding AEx to DDP on the mean FMA-UE, WMFT, and SIS-hand item rating and the average SIS-recovery scores (PROC GLM, SAS v9.4). Additionally, data describing the effect of AEx+DDP on UE impairment and function will be used to generate effect sizes for future research proposals. Pre- and post intervention PAS assessment will be tested with a student's T-test or Wilcoxon rank-sum test based on distributional assessment. The acute (within session) and training (over the course of intervention) effect of AEx on BDNF and DDP on CME will be assessed with a generalized mixed model analysis (PROC MIXED). Relationships of biomarkers of plasticity (PAS, BDNF, CME) and response to AEx+DDP (change in FMA-UE or WMFT) will be explored with Pearson or Spearman-rank order correlational analysis, depending on distributional assessment (Aim 3).

**Confidentiality:** All records regarding participation in this study will be kept in locked file cabinets in the appropriate laboratories and/or offices, and stored on MUSC network storage. Access to linked identifiers is limited to research personnel intimately involved with the human subjects. All data and records acquired from subjects is for research purposes only and will be kept confidential and maintained in a secure database identifiable only by subject code. The results of the study may be published for scientific purposes; however, subjects' identities will not be revealed and data will not be traceable to any individuals in any resultant publications. The information gathered during this study will be kept confidential to the extent permitted by law.

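### The MEP change at sessions 2, 10 and 17 is credited to DDP, but each is an AEx-then-DDP session and no CME reference separates the two components

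*Combined protocol and SAP*

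**What the plan says.** In section 9.0, Neurophysiological Assessments, the item on DDP-induced CME opens with "The effect of DDP on CME will be assessed in the paretic UE". A bin of twenty MEPs is collected "Before and after DDP on 3 occasions (DDP sessions 2, 10, and 17"), and the item closes by saying that these data will describe "the direct effect of a single and multiple sessions of DDP on the corticomotor pathway of the paretic UE". It also states an expectation that DDP will increase CME if recovery works through a stronger corticomotor pathway.

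The Statistical Analysis Plan in section 11.0 carries the same attribution into the model: "The acute (within session) and training (over the course of intervention) effect of AEx on BDNF and DDP on CME will be assessed", using a mixed model.

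Other parts of the document bear on this:

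- Section 9.0, Project Overview: "Subjects will complete 15 minutes of AEx prior to DDP". Intervention visits describes all 18 sessions as AEx + DDP.
- Section 2.0, Background: a bout of AEx can raise CME, in chronic stroke as well as in control subjects.
- Section 3.0: AEx is there as a primer meant to strengthen the effect of DDP.
- Section 11.0, Power Analysis: no DDP-only group is enrolled. The historical DDP comparison in the SAP covers FMA-UE, WMFT and SIS, not CME.
- Section 1.0, Aim 3: the acute target is stated as the effect of AEx+DDP on plasticity biomarkers.

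**The concern.** The measurement item and the SAP name DDP as the cause of the CME change. The sessions being measured contain two components, and the protocol itself says that the other one also moves CME. Nothing in the plan observes CME under DDP without AEx, or under AEx without DDP.

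Followed as written, the plan would report a rise, a fall or no change in MEP amplitude as evidence about DDP, although AEx may have contributed. This matters because section 1.0 names the mechanisms of AEx-primed rehabilitation as a gap in the literature, and because CME is one of the biomarkers that Aim 3 correlates with clinical response. The question is what the CME contrasts may be called, and whether the label in Aim 3 already fits them better.

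**Working it through.** This is a question of identifiability, so the plan has no figure to reproduce. The across-session and within-session contrasts are taken in turn.

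**Across sessions (training effect).** Inputs: CME at sessions 2, 10 and 17; 15 minutes of AEx per session (Project Overview); goal dose of 200 DDP repetitions per session (Intervention visits).

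Prior bouts = session number − 1, assuming none is missed.

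| Session | Prior AEx bouts | Prior DDP bouts | Cumulative AEx (15 × bouts) | Cumulative DDP goal (200 × bouts) |
|---|---|---|---|---|
| 2 | 1 | 1 | 15 min | 200 |
| 10 | 9 | 9 | 135 min | 1,800 |
| 17 | 16 | 16 | 240 min | 3,200 |

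The last two columns are proportional (200/15 = 1,800/135 = 3,200/240 ≈ 13.3), so their correlation is 1. A missed visit removes one bout of each, so the bout counts stay equal. A reduced DDP dose, which the therapist may allow, would disturb the repetition totals but not the bout counts, and would not be a planned contrast.

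**Both effects in one model.** Take three sessions × two bins = 6 observations, with five fixed terms: intercept, acute AEx, acute DDP, cumulative AEx, cumulative DDP.

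- First bin before AEx: acute AEx and acute DDP are the same column (0 before, 1 after), and the two cumulative terms are the same column. Rank 3 of 5.
- First bin after AEx: acute AEx is present at every observation and merges with the intercept; the cumulative terms are again identical. Rank 3 of 5.

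The cumulative terms are aliased under either timing, and no choice of mixed-model options recovers them.

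**Within session (acute effect), first bin after AEx.** If the AEx effect is constant from the first bin to the second, it cancels, and the difference is the change across DDP. If it changes with time since AEx, a time term is needed. With intercept, time since AEx (0 and 60 minutes, taking DDP as about an hour) and acute DDP, the rank is 2 of 3, because the time column is 60 times the DDP column. An AEx-by-DDP interaction has the same problem: every second bin is DDP after AEx, so the interaction column equals the DDP column.

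**What the timing figures can bear.** The document says "It is expected that AEx + DDP sessions will last approximately 90 minutes" and that "subjects enrolled in our previous studies have averaged 200 self-selected repetitions per day, achieved in ~1 hours without adverse event". Hence 90 − 15 − 60 ≈ 15 minutes for everything else: vital signs, any TMS set-up, two MEP bins and any move between laboratories. That does not fix when either bin falls. Because "DDP will be dosed based on the number of repetitions performed", the interval to the second bin will also vary between participants and sessions.

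**Other CME data.** The PAS assessments are made at Pre Visit 3 and Post Visit 2, around the whole intervention, so they do not separate the components.

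**The case against.** The strongest reply concerns the acute contrast. Bins before and after DDP, in a session where AEx comes first, naturally bracket DDP alone, so the initial AEx rise is already in the baseline. That stands. What remains is a possible change in the AEx effect during DDP, plus any interaction, and the documents give no time course for MEP amplitude after AEx.

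A reader might infer more: that the AEx effect wears off between the two bins and so biases the result. The text does not support this. The 60-minute duration in Preliminary Data refers to neuroplastic potential, not raw MEP amplitude, and the session timings do not locate the bins. If decay did occur, it would lower the second bin and work against the increase the protocol expects, so a false positive should not be presumed either. Nor should the unstated order of the first bin and AEx be counted as an omission, since the study timeline figure is not available here.

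It can also be said that this is wording: direct may be meant as a contrast with PAS, sessions of DDP may be shorthand for the combined sessions, and the lack of a DDP-only group is disclosed. That is fair for the single word, but the opening statement of the item and the SAP still name DDP as the cause. The reply does not touch the across-session aliasing.

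**Conclusion.** The plan attributes to DDP a CME change that its design can attribute only to the combined intervention.

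- Training trend: inseparable from AEx on any reading, with 1, 9 and 16 prior bouts of each component if none is missed.
- Acute contrast: a possible, unquantified mixture. It rests on the assumption that the first bin follows AEx. It estimates the change across DDP performed after AEx, and would isolate a DDP step only if the AEx effect were constant over that hour and there were no interaction.

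No size or direction of bias can be given from the documents. A reader might infer that the study's main conclusion is weakened; it is not. CME is an exploratory Aim 3 outcome in a pilot of 10, and the primary feasibility and tolerability aim does not depend on it. The change is still worth making, because it alters what the trial can claim about mechanism and costs almost nothing.

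**What to change.** In the DDP-induced CME item of section 9.0 and in the SAP:

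1. For the acute contrast, replace the direct effect of DDP, and DDP on CME, with: *CME change across DDP performed after AEx (not attributable to DDP alone)*.
2. For the training trend over sessions 2, 10 and 17, use: *AEx+DDP effect*, in line with the combined label in Aim 3.
3. State that the first bin is collected after AEx and before DDP.
4. Record the minutes from the end of AEx to each bin, to be reported or used descriptively.

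A fixed AEx-to-DDP interval should not be imposed. It would constrain when DDP starts after the primer at three sessions, leave the second interval variable, and identify nothing new. An extra bin before AEx would make the acute AEx and DDP steps separately estimable (rank 3 of 3) only if the AEx effect stayed constant during DDP (rank 3 of 4 otherwise), and would not help the training trend, so it does not replace the relabelling.

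The cost is a few sentences and two recorded intervals at each of three sessions, with no added bins, visits or participants. The downside is that the DDP-only mechanistic claim is given up.
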